**NCT03799484**

**Version Date:** 11/30/2018

**Title:** Randomized, Single Center, Masked Study Comparing the Efficacy of Botulinum Toxin Type A Injection After Topical Anesthesia versus Petrolatum Ointment

**Principal Investigator:** [name]

**Biostatistician:** [name]

**Study Coordinator:** [name], BS

**Population:** Sample size ~14, male/female, 18 – 65 years of age, diagnosed with forehead rhytides electing for treatment with botulinum toxin Type A

**Number of sites:** 1, Robert Cizik Eye Center

**Study Duration:** Patient participation time will be approximately 16 weeks

### **Background:**

Botulinum toxin type A (BTX-A) is a potent neurotoxin that blocks the presynaptic acetylcholine release at the neuromuscular junction, causing a dose-dependent weakness or paralysis of skeletal muscle. Recovery of muscle function occurs through proximal axonal sprouting and muscle re-innervation by formation of a new neuromuscular junction. Botulinum toxins are currently used for the treatment of a variety of medical disorders including spastic facial conditions (essential blepharospasms, hemifacial spasms), strabismus, sphincter dysfunction, hyperlacrimation, hyperhidrosis and headaches (1-4). In addition, botulinum toxin has been used in the treatment of facial rhytides such as crow's feet, and glabellar lines with great aesthetic results (5, 6). More recently, the US Food and Drug Administration approved the use of Botox for the temporary improvement in the appearance of moderate to severe forehead lines associated with frontalis muscle activity in adults.

A number of factors have been postulated that may affect the efficacy and duration of action of botulinum toxin type A including reconstitution process, dilution (units per volume), storage time after reconstitution and depth of administration (7,8). The use of topical anesthetic prior to administration of BTX-A for the treatment of facial cosmetic rhytides and blepharospasm has been proposed to have a deleterious impact on BTX-A effect, but the data is very limited (7). Multiple studies have investigated the use of

topical vibration, topical ice, vapocoolants and topical anesthesia as methods to decrease the pain associated with the injection of BTX-A (9-12) without decreasing the efficacy of BTX-A. However, there is no consensus on standard of care for administration of anesthesia prior to BTX-A administration. While many surgeons use one or a combination of the anesthetizing methods above to decrease pain associated with the injection, others use none.

## **OBJECTIVES**

The objective of this study is to determine whether there is a difference in clinical effect (weakness/paralysis of the frontalis muscle), duration of effect, level of discomfort and patient satisfaction in patients receiving topical anesthesia (2.5% lidocaine/2.5 % prilocaine cream, Impax Laboratories, LLC) on one side of the forehead and petrolatum ointment on the other prior to BTX-A administration for the treatment of forehead rhytides.

## **Outcome Variables**

- Primary outcome variable is change of eyebrow excursion on each side of the forehead from baseline to each follow-up visit.
  
- Secondary outcome variables
  - Duration of effect, defined as the elapsed time from injection to the end of botulinum, such that return of baseline frontalis function, i.e. within 2 mm of baseline value
  - Perception of pain immediately after injection at each side
  - Patient satisfaction for each side
  - Patient's perception of difference in efficacy

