## **Sample Size Calculations**

This study is design to compare change of eyebrow excursion from baseline at each side of forehead. Tzou (2005) reported that the standard deviation of eyebrow excursion was 2.31 mm in both European and Asian populations (16). To detect a 2 mm differences between 2 sides, a sample size of 14 is required to have 5% significance level and 90% power.

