## Scheduled Follow-up Visits

Participants will follow-up 2 weeks (+/- 3 days), 6 weeks (+/- 2 weeks) and 16 weeks (+/- 2 weeks) after the injection.

Table 1. Time Windows for Scheduled Follow-up Visits (number of days after injections)

Follow-Up Visit	Ideal Follow-up Time	Visit Window
Week 2	14 days	11 days – 17 days
Week 6	42 days	35 days – 49 days
Week 16	112 days	98 days – 126 days

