### **Brow Excursion**

Brow excursion will be assessed at Baseline, Week 2, Week 6 and Week 16. Visits. Examinations will be performed by a masked examiner. Eyebrow excursion will be measured by using a purple marking pen and placing a mark just above the brow, parallel to the center of the pupil while the participants is in a relaxed neutral expression. Then, the participant will then be asked to raise the brows and the excursion of the brow from resting position to maximum elevation will be measured in millimeters.

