### **Data Analysis**

Data will be summarized by mean (SD) and compared for continuous variables, e.g. age, eyebrow excursion, etc., and frequency (%) for discrete variables, e.g. sex, end of effect at each follow up, etc. Eyebrow excursion and patient satisfaction at each follow up as well as duration of effect and pain score will be compared between the topical anesthetic pretreated and non-pretreatment groups using paired t-test; while percent of end of effect at each follow-up visit, rate of complications and subjective pain will be compared using McNemar test.

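### The primary outcome is tested at three visits with no primary visit or decision rule, so the stated 5% level is not secured

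*Combined protocol and SAP*

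**What the plan says.** - **Outcome Variables:** "Primary outcome variable is change of eyebrow excursion on each side of the forehead from baseline to each follow-up visit". No visit is singled out.
- **Brow Excursion:** "Brow excursion will be assessed at Baseline, Week 2, Week 6 and Week 16". Each follow-up visit therefore means three post-injection time points; Scheduled Follow-up Visits and Table 2 agree.
- **Data Analysis:** "Eyebrow excursion and patient satisfaction at each follow up" are among the measures set against each other for the two sides, and the method named for them is the paired t-test. This gives one paired t-test of the primary measure per visit. The section refers to excursion rather than its change from baseline, but the count of three tests is the same.
- **Sample Size Calculations:** for a 2 mm difference between sides, "a sample size of 14 is required to have 5% significance level and 90% power". Neither the level nor the difference is attached to a visit.
- **Objectives:** "The objective of this study is to determine whether there is a difference in clinical effect". The question has no direction, so the tests are taken as two-sided; the plan does not state sidedness.

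No section gives a primary visit, an order of testing, a repeated-measures or other joint test, a multiplicity adjustment, or a requirement that all visits agree.

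**The concern.** The plan will yield three p-values of equal primary standing and one declared error rate. Without a rule linking them, a single significant visit could be taken as evidence that topical anesthetic alters the toxin's effect, and the 5% level would then not describe the chance of a false claim.

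The visits may well disagree. Duration of effect, defined by return towards baseline function, is a separate secondary outcome, so an early and a late difference between sides would mean different things. The 2 mm calculation cannot be matched to a visit either, so the power for the primary claim is undefined as well. The Background describes existing data on this question as very limited, so an isolated positive result from about 14 participants could carry more weight than it deserves.

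**Working it through.** **Inputs from the protocol.** 14 participants, each contributing one pair of sides; 5% level; 90% power; 2 mm difference; SD 2.31 mm (Sample Size Calculations); three follow-up visits; paired t-test at each.

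**Assumed.** Two-sided tests. The correlation r of the between-side difference across visits is not given and is varied.

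**1. The plan's own figure.** Normal approximation for a paired comparison, with 2.31 mm used as the SD of the between-side difference:

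n = [2.31 × (1.960 + 1.282) / 2]² = 14.02

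This matches the stated 14 (normal-approximation power at 14 is 89.97%). The calculation is therefore for one test at one two-sided 5% level. With the planned paired t-test (noncentral t, 13 df), power for that single test at n = 14 is 84.9%.

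**2. Limits for three tests.** With no true difference at any visit:

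- independent visits: 1 − 0.95³ = 14.26%
- any correlation: at most 3 × 5% = 15%

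**3. Correlated visits.** Null trials were simulated (400,000 per setting, 14 pairs, critical value |t| > 2.160, simulation standard error at most 0.06 percentage points). The table gives the chance of at least one p < 0.05. In the second pattern, r applies to adjacent visits and r² to the first and last.

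| r | Equal correlation | First-order autoregressive |
|---|---|---|
| 0 | 14.3% | 14.2% |
| 0.3 | 13.7% | 13.9% |
| 0.5 | 12.8% | 13.2% |
| 0.7 | 11.3% | 11.7% |
| 0.8 | 10.2% | 10.6% |
| 0.9 | 8.7% | 9.1% |
| 0.95 | 7.5% | 7.9% |
| 0.99 | 6.1% | 6.3% |

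**4. A reference point for r.** All three changes subtract the same baseline. If the between-side differences at baseline and at each follow-up are independent with variance σ², each change has variance 2σ² and any two share covariance σ², so r = σ²/2σ² = 0.5. Simulating that model gives 12.8%.

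**5. What the remedies do** (n = 14; powers use 2.31 mm as the SD of the between-side difference at each visit):

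- *One named visit:* error 5%; power 84.9% for 2 mm at that visit.
- *Bonferroni, 0.05/3 = 0.0167 per visit:* any-visit error 2.7% to 5.0% over r from 0.95 to 0; per-visit power falls to about 69%.
- *One test of the three-visit mean:* error 5%; SD = 2.31 × √[(1 + 2r)/3]. If 2 mm is present at one visit only, the mean difference is 2/3 = 0.67 mm and power is 23% at r = 0.5 (41% at r = 0, 17.5% at r = 0.95). If 2 mm is present at all three visits, power is 95.6% at r = 0.5 (99.9% at r = 0, 86% at r = 0.95).

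**The case against.** The best reply is that the inflation depends on a rule the plan never states. Nowhere does it say that one significant visit will be claimed as a difference. The objective covers both size and duration of effect, so the comparisons can be read as a description over time in which each test keeps its own 5%. If all three visits had to be significant, the false-claim chance would be far below 5% (0.01% at r = 0, 2.8% at r = 0.95). The ends of the correlation range are also arbitrary: zero is extreme for the same foreheads measured against one baseline, and at 0.99 the chance is only about 6%.

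These points limit the figure but do not remove the defect. The plan excludes neither the any-visit nor the all-visits reading, yet it declares a primary outcome, a 5% level and 90% power. Those terms have no meaning until the decision rule is written down. High correlation reduces the inflation without abolishing it.

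It is also fair to say that the three-visit mean should not be judged only on a difference confined to one visit. For a constant 2 mm difference at r = 0.5 it has more power than a single named visit. Choosing between them is a real trade-off for the investigators.

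**Conclusion.** The concern holds. As written, the plan runs three unadjusted primary tests under one stated 5% level, with no rule for combining them. That omission is certain from the text. Its size is conditional: about 8% to 14% instead of 5% if significance at any one visit is claimed, for assumed correlations from 0.95 down to 0, and never above 15%. The shared-baseline model puts it near 13%. The inflation is moderate and cheap to remove, so it should be settled before outcome data are seen.

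**What to change.** Name one primary visit, chosen by the investigators on clinical grounds before data are seen.

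- **Outcome Variables**, add: *The primary comparison is the between-side difference in change in directly measured eyebrow excursion (mm) from baseline to Week X (X being one of 2, 6 or 16), by paired t-test at the two-sided 5% level.*
- **Data Analysis**, add: *Comparisons at the other two visits are secondary and are reported as estimates with 95% confidence intervals.*
- **Sample Size Calculations**: attach the 2 mm difference to the same visit.

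The core change is two sentences, with no extra patients or visits. Its price is that a difference seen only at another visit is supportive, not confirmatory.

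Two alternatives also hold 5%:

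- *A fixed testing order across visits*, stopping at the first non-significant result. A null result at the first visit ends confirmatory testing.
- *One test of each participant's mean between-side difference over the three visits.* This is efficient if the difference persists and weak if it is confined to one visit (the powers are in the working).

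As a related tidy-up, the photographic brow-elevation ratio has no stated test. Labelling it supportive would avoid a second candidate for the primary measure.

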### **Inclusion criteria**

Patients who meet the following inclusion criteria may be enrolled:

- Subjects 18 to 65 years of age
- Presence of horizontal forehead rhytides
- Good eyebrow excursion ( $\geq 5$  mm)
- Able to understand and sign an informed consent form that has been approved by the Committee for Protection of Human Subjects

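### The end-of-effect rule needs no prior loss of function, so a side counted at Week 2 is one with no recorded loss beyond 2 mm, not an observed recovery

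*Combined protocol and SAP*

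**What the plan says.** Under Outcome Variables, the first secondary outcome is "Duration of effect, defined as the elapsed time from injection to the end of botulinum", and the end is marked by "return of baseline frontalis function, i.e. within 2 mm of baseline value". The section does not define a responder, and no section says how to code a side that never weakened by more than 2 mm.

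The section on brow excursion fixes the measurement times: "Brow excursion will be assessed at Baseline, Week 2, Week 6 and Week 16". Table 1 gives the Week 2 window as "11 days – 17 days", with 14 days as the ideal. Nothing is measured between injection and that visit.

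Under Data Analysis, duration is compared between sides by paired t-test, and "percent of end of effect at each follow-up visit" is compared by McNemar test. Every follow-up visit includes Week 2.

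The inclusion criteria ask for "Good eyebrow excursion" of at least 5 mm at entry.

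**The concern.** The Background says that topical anesthetic has been proposed to impair the toxin's effect. The Objectives list clinical effect and duration of effect as separate questions. A side that responds weakly and a side that responds and then wears off early are therefore different findings, and the trial should be able to tell them apart.

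The end-of-effect rule does not separate them. A side that lost 0 to 2 mm at Week 2 already satisfies it. That side is counted as ended in the Week 2 McNemar comparison and, on a literal reading, receives about 14 days in the duration t-test. Applying one rule to both sides does not cancel this: if the anesthetic blunts response, the rule is met at Week 2 more often on the anesthetic side. Two secondary results are at stake. The Week 2 end-of-effect percentage would carry the wrong label, and the duration difference would be somewhat too small.

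**Working it through.** **The plan's own figure.** The SD used below comes from the sample size section, so that calculation is checked first. Inputs: difference 2 mm, SD 2.31 mm, 5% significance, 90% power. For a paired comparison by the normal approximation, two-sided:

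n = (SD × (1.960 + 1.282) / difference)² = (2.31 × 3.2415 / 2)² = 14.02.

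This agrees with the stated 14. The point below does not depend on it.

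**Step 1: the rule at the first visit (no assumptions).** A Week 2 loss of 0, 1 or 2 mm leaves the side within 2 mm of baseline, so the criterion is met. No earlier post-injection measurement exists that could have shown a larger loss. Hence every side counted as ended at Week 2 has no recorded loss beyond 2 mm, and none is an observed recovery.

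**Step 2: what such a side may be.** A 2 mm loss is 2/5 = 40% of the minimum eligible baseline, 2/8 = 25% of 8 mm and 2/10 = 20% of 10 mm. The group therefore includes partial responders as well as non-responders.

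**Step 3: how often.** The documents give no expected Week 2 loss. Assumptions:
- Losses are normally distributed.
- Mean loss is 5 mm on the petrolatum side and 3 mm on the anesthetic side. The 2 mm gap is the difference the trial is sized to detect.
- The SD of loss is 2.31 mm, which the plan reports for excursion, not for change. Values of 1.5 and 1.0 mm show the sensitivity.

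Share flagged at Week 2 = Φ((2 − mean loss) / SD).

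| SD (mm) | Mean loss 5 mm | Mean loss 3 mm | Expected sides of 14 |
|---|---|---|---|
| 2.31 | Φ(−1.30) = 0.097 | Φ(−0.43) = 0.333 | 1.4 vs 4.7 |
| 1.5 | Φ(−2.00) = 0.023 | Φ(−0.67) = 0.252 | 0.3 vs 3.5 |
| 1.0 | Φ(−3.00) = 0.001 | Φ(−1.00) = 0.159 | under 0.1 vs 2.2 |

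With mean losses of 4 and 2 mm and SD 2.31 mm, the shares are 0.193 and 0.500.

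The formula also counts the few sides that gain more than 2 mm. Excluding them subtracts Φ((−2 − mean loss) / SD). At SD 2.31 mm this takes 33% to about 32% (0.333 − 0.015), leaves 10% unchanged, and takes 50% to about 46%.

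**Step 4: effect on mean duration.** Suppose the flagged sides never go beyond a 2 mm loss later. Recoding them from 14 days to 0 then changes the mean side difference by 14 × (difference in shares):
- 5 vs 3 mm, SD 2.31: 14 × (0.333 − 0.097) = 3.3 days. Over the visit window this is 11 × 0.236 = 2.6 to 17 × 0.236 = 4.0 days.
- 5 vs 3 mm, SD 1.5: 14 × (0.252 − 0.023) = 3.2 days.
- 5 vs 3 mm, SD 1.0: 14 × (0.159 − 0.001) = 2.2 days.
- 4 vs 2 mm, SD 2.31: 14 × (0.500 − 0.193) = 4.3 days.

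**The case against.** The definition speaks of a return, and a return presupposes a loss. The 2 mm can then be read as the tolerance for judging that return, so a side that never weakened would have nothing to return from. The plan also contains no rule that assigns duration to the first qualifying visit; the 14-day value is inferred. Both points stand. However, the measurable criterion that follows the word does not carry the requirement, an analyst would code the criterion, and the plan offers no other coding for such a side.

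The effect on duration is modest. A shift of 3 to 4 days is small beside nominal gaps of 28 and 70 days between visits, and the affected sides already receive the shortest duration the schedule allows. Weak response is also visible directly in the primary outcome, change in excursion at each visit. These points stand too, and they keep the issue at the level of secondary outcomes.

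A simple onset condition would bring its own trouble. Week 2 has no earlier post-injection visit, so no side could end there and the Week 2 McNemar comparison would be empty. At Weeks 6 and 16, sides with no loss beyond 2 mm might be counted as not ended, alongside sides still weakened. This stands, and the fix has to cover Data Analysis as well as the definition.

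A reader might infer that every side flagged at Week 2 is a non-responder. The documents do not support that, because 2 mm can be 40% of an eligible baseline.

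**Conclusion.** The defect is real but limited. From the text and schedule alone, the Week 2 end-of-effect percentage cannot show observed recovery; it shows the absence of a recorded loss beyond 2 mm. That conclusion needs no assumption about response.

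The rest is conditional. The credit of about 14 days depends on a literal reading and the visit schedule. Frequency cannot be determined from the documents: under assumed mean losses of 5 and 3 mm, the petrolatum share runs from 0.1% to 10% and the anesthetic share from 16% to 33% across SDs of 1.0 to 2.31 mm. The resulting change in the mean duration difference is about 2 to 3 days, or 4.3 days with mean losses of 4 and 2 mm at the largest SD. The direction, a slightly smaller difference, holds only if the anesthetic does blunt response.

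A reader might go further and infer that the plan definitely books non-response as a completed two-week effect, or that the trial's main conclusion is biased. Neither follows. The plan has no explicit assignment rule, and the primary outcome does not use the end-of-effect definition.

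**What to change.** Keep the 2 mm threshold and amend two sections.

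**Outcome Variables.** Define duration as the time from injection to the first visit within 2 mm of baseline that follows a visit more than 2 mm below baseline. Code a side that is never more than 2 mm below baseline as duration 0, labelled *no loss beyond 2 mm*, and keep all pairs in the comparison.

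**Data Analysis.** At each visit, run the McNemar test on *effect absent at this visit*, meaning not more than 2 mm below baseline, for all sides. Week 2 is then not empty, and sides that never weakened beyond 2 mm are not grouped with sides still weakened. Report by side how many never exceeded a 2 mm loss and how many exceeded it and then recovered.

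**Cost.** A few sentences in two sections, using data already collected, with no change to visits or treatment. The duration data will contain zeros, and some partial responders with low baseline excursion will be coded 0; the separate count by side keeps both visible. The wording should be settled before any follow-up data are seen.

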## **STUDY DESIGN**

This is a prospective, randomized, double-masked, comparative study in patients who present at the Robert Cizik Eye Clinic with horizontal forehead rhytides requiring treatment with botulinum toxin Type A (Botox ®; Allergan, Irvine, CA, USA).

## **PARTICIPANTS**

All patients who meet the following eligibility criteria may be enrolled.

### **Inclusion criteria**

Patients who meet the following inclusion criteria may be enrolled:

- Subjects 18 to 65 years of age
- Presence of horizontal forehead rhytides
- Good eyebrow excursion ( $\geq 5$  mm)
- Able to understand and sign an informed consent form that has been approved by the Committee for Protection of Human Subjects

### **Exclusion criteria**

Patients who meet the following exclusion criteria may NOT be enrolled

- Previous injection of botulinum toxin in the intended treatment area for the study within the last 4 months
- Known allergy to botulinum toxin
- Known history of sensitivity to local anesthetics of the amide type
- Existing disorder of neuromuscular transmission (e.g. Myasthenia gravis or Lambert-Eaton syndrome)
- Usage of medication with effect on neuromuscular function
- Women of childbearing potential (who are not postmenopausal for at least 1 year or surgically sterile), who are pregnant or nursing or intend to become pregnant during the time of the study
- Significant brow asymmetry ( $> 5$ mm)
- Unable to follow-up for the duration of the study (16 weeks)

## **Masking**

The randomization information will only be known by the principal investigator performing the injections and will not be disclosed to the participants or the brow excursion examiner.

## **Sample Size Calculations**

This study is design to compare change of eyebrow excursion from baseline at each side of forehead. Tzou (2005) reported that the standard deviation of eyebrow excursion was 2.31 mm in both European and Asian populations (16). To detect a 2 mm differences between 2 sides, a sample size of 14 is required to have 5% significance level and 90% power.

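### The 90% power claimed for 14 participants is not what the planned paired t-test gives: about 85% if 2.31 mm is the SD of the paired difference, and the plan does not document that SD

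*Combined protocol and SAP*

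**What the plan says.** The Sample Size Calculations section says that the study compares change in excursion from baseline on each side. It cites a published report that "the standard deviation of eyebrow excursion was 2.31 mm in both European and Asian populations" and concludes: "To detect a 2 mm differences between 2 sides, a sample size of 14 is required to have 5% significance level and 90% power". It gives no formula, does not say whether the test is one- or two-sided, and states no correlation between sides or between visits.

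Three other sections bear on this:

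- **Outcome Variables:** "Primary outcome variable is change of eyebrow excursion on each side of the forehead from baseline to each follow-up visit".
- **Data Analysis:** excursion at each follow-up "will be compared between the topical anesthetic pretreated and non-pretreatment groups using paired t-test".
- **Objectives:** "The objective of this study is to determine whether there is a difference in clinical effect", which names no direction.

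**The concern.** There are two separate problems.

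First, a power statement should describe the test that will be run. With 14 pairs, the SD of the differences is estimated on 13 degrees of freedom, and a normal approximation that treats it as known overstates power noticeably.

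Second, a paired t-test depends on the SD of the within-person difference. Here that means the difference between sides in change from baseline. The plan offers an SD for excursion itself, which is a different quantity.

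The power figure is the only justification given for the sample size. A non-significant result could be read as showing that the anesthetic cream does not weaken the toxin's effect. How far that reading is warranted depends on the chance of missing a true 2 mm difference. The plan puts that chance at 10%.

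**Working it through.** **Inputs**

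| Input | Value | Source |
|---|---|---|
| Difference to detect (δ) | 2 mm | Sample Size Calculations |
| SD | 2.31 mm, described as the SD of excursion | Sample Size Calculations |
| Significance level, power | 5%, 90% | Sample Size Calculations |
| n | 14 people, both sides each | Sample Size Calculations |
| Test | Paired t-test | Data Analysis |
| Sidedness | Two-sided (assumption) | Inferred from Objectives |

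**Step 1: reproduce the plan's figure.** Take 2.31 mm as the SD of the paired difference and use the normal approximation:

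n = (z₀.₉₇₅ + z₀.₉₀)² × (SD/δ)² = (1.960 + 1.2816)² × (2.31/2)² = 14.02.

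Normal-theory power at n = 14 is 89.97%. This matches the stated 14 and 90%. Strict rounding up would give 15.

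**Step 2: the planned test on the same inputs.** For a two-sided paired t-test at n = 14:

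- degrees of freedom = 13, critical t = 2.160
- noncentrality = (2/2.31) × √14 = 3.24
- power from the noncentral t distribution = 84.9% (a simulation of 400,000 trials gives 85.0%)

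| n | 14 | 15 | 16 | 17 |
|---|---|---|---|---|
| Power | 84.9% | 87.6% | 89.9% | 91.8% |

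The smallest n with at least 90% power is 17. With n held at 14, 90% power is reached for δ of about 2.17 mm at SD 2.31 mm, or for a paired SD of about 2.13 mm at δ = 2 mm.

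**Step 3: other readings of the stated figure.**

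- One-sided 5% paired t-test: 92.2% power at 14. The smallest n for 90% is 13 (90.2%).
- One-sided normal approximation: n = 12.
- Two independent samples: 29 per group.

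None of these gives 14. The two-sided normal formula is the closest match.

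**Step 4: how much depends on the SD.** Power at n = 14 for δ = 2 mm, two-sided paired t-test, over an assumed range of paired SDs:

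| Paired SD (mm) | 1.75 | 2.0 | 2.13 | 2.31 | 2.5 | 2.75 | 3.0 |
|---|---|---|---|---|---|---|---|
| Power | 97.6% | 93.2% | 90.0% | 84.9% | 79.0% | 71.1% | 63.6% |

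Suppose 2.31 mm were the SD of change on one side, with correlation ρ between sides. Then the paired SD = 2.31 × √(2(1 − ρ)), which equals 2.31 mm only when ρ = 0.5. Power at n = 14 would be 56% at ρ = 0, 69% at 0.25, 85% at 0.5, 92% at 0.6 and 97% at 0.7. Reaching 90% needs ρ of about 0.57 or more. These correlations are assumptions, since the plan gives none.

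If 2.31 mm is the SD of excursion at a single visit, as the text literally says, the between-visit correlation is needed as well.

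**The case against.** The arithmetic is not in dispute. The case on the other side is about certainty and weight.

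*Two-sidedness and the role of the SD are both inferred.* This is true. A one-sided 5% test would make the claim conservative, at 92.2%. But nothing in the plan supports one-sided testing, and that reading would have called for 13 participants. The role of the SD is recovered by working back from 14. That is why the 85% is conditional.

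*True power may be 90% or more.* It may, if the paired SD is about 2.13 mm or less. The plan does not exclude this, but gives nothing to support it either. What follows is that the 90% has no documented basis, not that power is certainly below it.

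*The SD matters more than the choice between z and t.* This stands. The t correction costs about 5 points, while plausible SDs move power much further. Restating 85% discloses the SD assumption without resolving it, so the sensitivity line is an essential part of the correction.

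*The Data Analysis section speaks of excursion at follow-up, not change from baseline.* This affects which SD is needed: taken literally, it removes the need for the between-visit correlation. It does not affect the result in step 2.

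*The practical effect is small.* On these inputs the difference detectable with 90% power moves only from 2 mm to about 2.17 mm. That argues against adding participants, but not against correcting the sentence.

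**Conclusion.** The concern holds, and the power statement is wrong as written. On the plan's own inputs, with 2.31 mm used as the paired SD, the planned test has 84.9% power at n = 14. The chance of missing a true 2 mm difference is therefore about 15%, not 10%, and 90% power would take 17 participants.

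This rests on a two-sided 5% test, which is well supported by the objective but not stated. It also rests on 2.31 mm being the SD of the within-person difference, which is not documented. If it is not that SD, the 90% cannot be checked from the plan, and actual power may lie on either side of 85%. The correction should be made, but it does not call the design into question.

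**What to change.** Keep 14 participants and replace the power sentence. Suggested wording:

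> With 14 participants, a two-sided 5% paired t-test has about 85% power to detect a 2 mm between-side difference in change from baseline (90% power for about 2.17 mm), assuming the SD of the paired difference is 2.31 mm. The cited SD is for eyebrow excursion; its use for the paired difference is an assumption. Power would be 93% for a paired SD of 2.0 mm, 90% for 2.13 mm, 79% for 2.5 mm and 64% for 3.0 mm.

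A further clause can give power at SD 2.31 mm with fewer completers: about 82% with 13 and 78% with 12. These numbers are illustrations only. The Exclusion criteria already rule out anyone "Unable to follow-up for the duration of the study (16 weeks"), and a late loss would not affect the week 2 comparison.

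The cost is one paragraph of protocol text, with no extra participants and no change to procedures or analysis. The stated power becomes slightly less favourable, and the rewording makes the claim accurate without raising the power.
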